## **7.0 SAFETY ANALYSES**

Since this is an observational study with no intervention, no formal safety analysis is planned. Overdoses and deaths will be tracked from the safety event reporting.

[figure not shown]
### **7.1.1 Adverse Events (AEs) and Serious Adverse Events (SAEs)**

For purposes of this study only overdoses, whether hospitalized or not, and all deaths will be collected. At weeks 1, 4 and 8, research staff will ask about any overdoses that have occurred since the last study contact. Additionally, any deaths from any cause will be reported on the AE form. No other AEs or SAEs will be captured in the course of this observational study. Reporting definitions and procedures are outlined in the Manual of Operations.

Each of the study sites has established practices for managing medical and psychiatric emergencies, and the study staff will continue to utilize these procedures. Treatment providers at each site will be responsible for monitoring participants for possible clinical deterioration or other problems, and for implementing appropriate courses of action.

**Figure 1: Diagram of Participant Enrollments**

Table 1: Summary of Consents, Eligible Screens and Enrollments					
CTP	Number of Consents	Number of Eligible Screens	Number Enrolled	Percent of Consents Enrolled	Percent of Eligible Screens Enrolled
OV Maryhaven					
FL Gateway Community Services					
PA Tarzana Treatment Centers					
NEC Stanley Street Treatment and Resources (SSTAR)					
GNV Bellevue Hospital Center					
Total					

Table 2: Summary of Screen Failures						
	OV Maryhaven	FL Gateway Community Services	PA Tarzana Treatment Centers	NEC Stanley Street Treatment and Resources (SSTAR)	GNV Bellevue Hospital Center	Total
Number of consented						
Number of screen failures						
Reasons for Screen Failure* (n (%))						
18 years of age or older						
Opioid use disorder						
Opioid use past 30 days						
Seeking opioid dependence treatment						
Able to provide written informed consent						
Able to speak English/provide consent						
Severe medical, psychiatric, substance use condition						
Has suicidal or homicidal ideation						
On methadone maintenance						
Pain requiring opioid tx						
Pending legal action						
Pregnant/breastfeeding						
Participated in CTN-0051						
Participant discharged to the community						

Table 3: Summary of Participant Disposition						
	OV Maryhaven	FL Gateway Community Services	PA Tarzana Treatment Centers	NEC Stanley Street Treatment and Resource	GNV Bellevue Hospital Center	Total
Number of Enrolled Participants						
Number of Study Completers  - N (%)						
Number of Early Terminations - N (%)						

---

 Study completers are defined as participants who have completed the Week 8 visit.

**Table 4: Summary of Baseline Characteristics by CTP**

Characteristic	OV Maryhaven	FL Gateway Community Services	PA Tarzana Treatment Centers	NEC Stanley Street Treatment and Resource	GNV Bellevue Hospital Center	Total
Gender						
Missing						
Male						
Female						
Participant chose not to answer						
Age (Mean(Std))						
Age						
Missing						
< 18						
18 - < 25						
25 - < 35						
35 - < 45						
45 - < 55						
55 - < 65						
65 - < 75						
75+						
Ethnicity						
Not Hispanic or Latino						
Hispanic or Latino						
Missing						
Participant chose not to answer						
Race						
Missing						
American Indian or Alaska Native						
Asian						
Black or African American						
Native Hawaiian or Pacific Islander						
White						
Other						
Multiracial						
Unknown						
Participant chose not to answer						

**Table 4: Summary of Baseline Characteristics by CTP**

Characteristic	OV Maryhaven	FL Gateway Community Services	PA Tarzana Treatment Centers	NEC Stanley Street Treatment and Resource	GNV Bellevue Hospital Center	Total
Education completed						
Less than high school diploma						
High school graduate						
GED or equivalent						
Some college, no degree						
Associate's degree: occupational, technical, or vocational program						
Associate's degree: academic program						
Bachelor's degree						
Master's degree						
Professional school degree						
Doctoral degree						
Don't know						
Refused						
Marital status						
Married						
Widowed						
Divorced						
Separated						
Never married						
Living with partner						
Refused						
Don't know						
Employment						
Working now						
Only temporarily laid off, sick leave, or maternity leave						
Looking for work, unemployed						
Retired						
Disabled permanently or temporarily						
Keeping house						
Student						
Other						

Table 5: Summary of Subgroups of Interest by CTP						
Subgroups of Interest	OV Maryhaven	FL Gateway Community Services	PA Tarzana Treatment Centers	NEC Stanley Street Treatment and Resource	GNY Bellevue Hospital Center	Total
Treatment Type Received Post-Discharge						
Medication-assisted Treatment						
No Medication-assisted Treatment						
Length of Stay						
≤7 days						
8-20 days						
≥ 21 days						
Baseline Opioid Severity Level*						
Low Severity						
High Severity						
Baseline Opioid Severity Level/ Treatment Type Received Post-Discharge						
Low Severity/ Medication-assisted Treatment						
Low Severity/ No Medication-assisted Treatment						
High Severity/ Medication-assisted Treatment						
High Severity/ No Medication-assisted Treatment						
Baseline Opioid Severity Level*						
Low Severity/ ≤7 days						
Low Severity/ 8-20 days						
Low Severity/ ≥ 21 days						
High Severity/ ≤7 days						
High Severity/ 8-20 days						
High Severity/ ≥ 21 days						

\* To compute the opioid severity level, if the primary opioid of use in the last 7 days was not heroin or the route of administration is not IV-injection then that participant is defined as a low severity user. For IV heroin users where the quantity is not provided in bags but in dollars, bags are estimated as the dollar amount/10 rounded to the nearest integer.

**Table 6: Summary of Adverse Events by CTP**

	OV Maryhaven	FL Gateway Community Services	PA Tarzana Treatment Centers	NEC Stanley Street Treatment and Resource	GNV Bellevue Hospital Center	Total
Number of Enrolled Participants						
Number of Participants with Adverse Events						
Number of Adverse Events						
Adverse Event Type						
Overdose						
Overdose resulting in death						
Other death						
Severity of Adverse Event						
Grade 1-Mild						
Grade 2-Moderate						
Grade 3-Severe						
Relationship of Adverse Event						
Not Related						
Related						

Note: for the purposes of this study, only overdoses, whether hospitalized or not, and all deaths were collected

**Table 7: Listing of Adverse Events by CTP**

CTP	Participant ID	AE Description	Onset Date	Severity of Overdose	Opioids Involved	Primary Cause of Death	Aware Date	Hospitalization

[figure not shown]
Table 8: Summary of Time to First Use by Type of Treatment Received Post-Discharge			
	Treatment Type Received Post-Discharge		
	Medication-assisted Treatment	No medication-assisted Treatment	Total
Number of Participants			
Any Opioid Use			
Yes			
No			
Time to First Use  (days)			
N			
Mean			
SD			
Median			
Min			
Max			

---

 Time to first use summary statistics are only summarized for subjects who reported any opioid use on TLFB.

**Figure 2:** Kaplan-Meier Plots of Time to First Use by Type of Treatment Received

*Example Kaplan-Meier figure provided below.*

The x-axis for the Time to First Use Kaplan-Meier Plots will be measured in days. Separate curves on the same plot will be defined as the types of treatment received. Censored observations will be represented using a + sign.

[figure not shown]
Table 9: Summary of Time to First Use by Length of Stay				
	Length of Stay			
	≤7 days	8-20 days	≥21 days	Total
Number of Participants				
Any Opioid Use				
Yes				
No				
Time to First Use  (days)				
N				
Mean				
SD				
Median				
Min				
Max				

---

 Time to first use summary statistics are only summarized for subjects who reported any opioid use on TLFB.

**Figure 3:** Kaplan-Meier Plots of Time to First Use by Length of Stay

*Example Kaplan-Meier figure provided below.*

The x-axis for the Time to First Use Kaplan-Meier Plots will be measured in days. Separate curves on the same plot will be defined as the length of stay categories. Censored observations will be represented using a + sign.

[figure not shown]
Table 10: Summary of Time to First Use by Baseline Opioid Use Severity			
	Baseline Opioid Use Severity		
	Low Severity	High Severity	Total
Number of Participants			
Any Opioid Use			
Yes			
No			
Time to First Use  (days)			
N			
Mean			
SD			
Median			
Min			
Max			

---

 Time to first use summary statistics are only summarized for subjects who reported any opioid use on TLFB.

**Figure 4:** Kaplan-Meier Plots of Time to First Use by Baseline Opioid Use Severity

*Example Kaplan-Meier figure provided below.*

The x-axis for the Time to First Use Kaplan-Meier Plots will be measured in days. Separate curves on the same plot will be defined as the baseline opioid use severity. Censored observations will be represented using a + sign.

Table 11: Summary of Time to Regular Opioid Use by Type of Treatment Received Post-Discharge			
	Treatment Type Received Post-Discharge		
	Medication-assisted Treatment	No Medication-assisted Treatment	Total
Number of Participants			
Any Regular Opioid Use			
Yes			
No			
Time to Regular Use  (days)			
N			
Mean			
SD			
Median			
Min			
Max			

---

[figure not shown]
 Regular use is defined as seven consecutive opioid use days as reported on TLFB.

 Time to regular use summary statistics are only summarized for subjects who reported any opioid use on TLFB.

**Figure 5:** Kaplan-Meier Plots of Time to Regular Opioid Use by Type of Treatment Received

*Example Kaplan-Meier figure provided below.*

The x-axis for the Time to Regular Opioid Use Kaplan-Meier Plots will be measured in days. Separate curves on the same plot will be defined as the types of treatment received. Censored observations will be represented using a + sign.

Table 12: Summary of Time to Regular Opioid Use by Length of Stay				
	Length of Stay			
	≤7 days	8-20 days	≥21 days	Total
Number of Participants				
Any Regular Opioid Use				
Yes				
No				
Time to Regular Use  (days)				
N				
Mean				
SD				
Median				
Min				
Max				

[figure not shown]
---

 Regular opioid use is defined as seven consecutive opioid use days as reported on TLFB.

 Time to regular use summary statistics are only summarized for subjects who reported seven consecutive opioid use days on TLFB.

**Figure 6:** Kaplan-Meier Plots of Time to Regular Opioid Use by Length of Stay

*Example Kaplan-Meier figure provided below.*

The x-axis for the Time to Regular Opioid Use Kaplan-Meier Plots will be measured in days. Separate curves on the same plot will be defined as the length of stay categories. Censored observations will be represented using a + sign.

[figure not shown]
Table 13: Summary of Time to Regular Opioid Use by Baseline Opioid Use Severity			
	Baseline Opioid Use Severity		
	Low Severity	High Severity	Total
Number of Participants			
Any Regular Opioid Use			
Yes			
No			
Time to Regular Opioid Use  (days)			
N			
Mean			
SD			
Median			
Min			
Max			

---

 Time to regular opioid use summary statistics are only summarized for subjects who reported seven consecutive opioid use days on TLFB.

**Figure 7:** Kaplan-Meier Plots of Time to Regular Opioid Use by Baseline Opioid Use Severity

*Example Kaplan-Meier figure provided below.*

The x-axis for the Time to Regular Opioid Use Kaplan-Meier Plots will be measured in days. Separate curves on the same plot will be defined as the baseline opioid use severity. Censored observations will be represented using a + sign.

Table 14: Summary of UDS Results by Type of Treatment Received Post-Discharge			
	Treatment Type Received Post-Discharge		
	Medication-assisted Treatment	No Medication-assisted Treatment	Total
Number of Participants			
UDS Result (Baseline  )			
Negative			
Positive			
Missing			
UDS Result (Week 1)			
Negative			
Positive			
Missing			
UDS Result (Week 4)			
Negative			
Positive			
Missing			
UDS Result (Week 8)			
Negative			
Positive			
Missing			

---

 Day of Discharge into Community

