#### 3.2 Sample Size and Power Calculations

##### 3.2.1 Rationale for Sample Size and Statistical Power

No formal statistical hypothesis tests will be calculated for this study; therefore, there is neither sample size nor statistical power calculations. The study population is a convenience sample and it is anticipated that each participating site should be able to enroll approximately 60 participants for a total of approximately 360 participants. While the main objectives of this study are descriptive in nature, such as estimating the opioid use rate eight weeks after discharge to the community, it may be of interest to evaluate whether these opioid use outcomes are associated with certain covariates. Potential independent predictors of opioid use include: age, gender, race, ethnicity, use of medication-assisted treatment, and type of treatment received prior to discharge to the community.

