### 3.3 Software

All analyses will be performed utilizing SAS® version 9.3 or higher. All statistical tests will be conducted at the 5% Type I error rate (two-sided). When multiple tests are conducted, the chance of finding a significant difference in one of the tests, when in fact no difference exists, is greater than the stated Type I error rate. The investigators are aware of the multiple testing issues and will interpret results with caution and use confidence intervals where possible.

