## **5.0 STATISTICAL ANALYSES**

The primary objective of this study is to estimate opioid use rates, via various measures of use (Section 2), overall and separately for the sub-groups defined. Secondary exploratory analyses will involve modeling of opioid use as a function of certain independent predictors. For the primary objective all continuous variables (e.g., percent use days in the first week) will be summarized using the following descriptive statistics: *n* (non-missing sample size), mean, standard deviation, median, maximum and minimum. The frequency and percentages (based on the group-specific sample size) of observed levels will be reported for all categorical measures.

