## **6.0 MISSING DATA**

The number of missing as well as the number of positive and negative UDSs will be tabulated separately when calculating the UDS outcome at baseline, and weeks 1, 4 and 8. Analyses of self-reported use time to event outcomes (e.g. time to first use) will impute intermittent missing days as use, but will not impute missing days due to drop-out or loss-to-follow-up. When tallying the days of opioid use, all missing self-reported days will be imputed as positive. The number of days imputed for each subject will also be summarized.

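### Cheap improvement: times to first and regular opioid use are summarised only among participants with the event, and no pooled Kaplan-Meier curve, median or event percent is planned

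*SAP*

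**What the plan says.** SAP 5.0 gives the primary objective as to "estimate opioid use rates, via various measures of use (Section 2), overall and separately for the sub-groups defined". Days to first use and days to regular use are the first outcomes listed in SAP 2.0.

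For these time-to-event outcomes, SAP 6.0 "will impute intermittent missing days as use, but will not impute missing days due to drop-out or loss-to-follow-up". A participant lost before the event is therefore censored, and Figures 2 to 7 mark censored observations.

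The time rows (N, mean, SD, median, min, max) are restricted as follows:
- **Tables 8 to 10 (footnotes 2 to 4):** "Time to first use summary statistics are only summarized for subjects who reported any opioid use on TLFB".
- **Table 12 (footnote 8):** "Time to regular use summary statistics are only summarized for subjects who reported seven consecutive opioid use days on TLFB".
- **Table 13 (footnote 9):** "Time to regular opioid use summary statistics are only summarized for subjects who reported seven consecutive opioid use days on TLFB".
- **Table 11 (footnote 6):** the base named is any opioid use, unlike footnotes 8 and 9.

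The Kaplan-Meier figures are by subgroup. For Figures 2 and 5, "Separate curves on the same plot will be defined as the types of treatment received"; the others use length of stay or baseline severity. The list of figures has no pooled curve. No shell in Tables 8 to 13 has a row for a Kaplan-Meier median, a Kaplan-Meier percent or a confidence interval.

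Two sets of crude percents are planned with a Total column: the Yes/No rows of Tables 8 to 13, and the rows in Tables 17 to 19 for participants abstinent up to weeks 1, 4 and 8.

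**The concern.** A median taken among those who had the event answers a conditional question: when use began, among people seen to use. In a cohort where some never use within eight weeks, that is earlier than the day by which half the cohort has used. It also moves little with the event rate, so it hardly separates a cohort that does well from one that does badly. This is a descriptive study, and these are its first-listed outcomes. A reader who takes the Total column of Table 8 as the typical time to first use after discharge would be misled, and no pooled curve is planned to correct the impression. In the subgroup columns, the time rows would compress real differences in timing.

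**Working it through.** **Inputs from the documents.** Follow-up of about 8 weeks, taken as 56 days (protocol 6.2). Event proportions P of 60% and 70%, n = 360, and hazard ratios 1.47 and 1.45 (SAP 3.2.4, in-text Table 1). Background rates of 71% using opioids within six weeks and 65% using drugs within four weeks (protocol 4.1).

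**Assumed, not in the documents.** Event-time shape: Weibull with shape k from 0.5 to 2, where k = 1 is constant hazard. Random dropout of 20% or 30% by day 56.

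**1. The plan's own figures.** Read the table's SD column as the SD of a binary covariate, so that 0.5 means equal groups. Power = Φ(√(events/4) × ln HR − 1.96).
- 360 × 0.60 = 216 events, HR 1.47: Φ(7.348 × 0.385 − 1.96) = 80.8% (stated 82%).
- 360 × 0.70 = 252 events, HR 1.45: Φ(7.937 × 0.372 − 1.96) = 83.9% (stated 84%).

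Both agree to within 2 points, so these event proportions and hazard ratios are used below.

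**2. Overall median, full follow-up.** The event-only median is the P/2 quantile of the cohort distribution, that is, the 30th or 35th percentile, whatever the hazard shape. At constant hazard, λ = −ln(1 − P)/56, the cohort median is ln 2/λ, and the event-only median is −ln(1 − P/2)/λ.
- P = 60%: λ = 0.01636; cohort 42.4 days, event-only 21.8 (49% lower).
- P = 70%: λ = 0.02150; cohort 32.2 days, event-only 20.0 (38% lower).
- P = 40%: cohort median not reached by day 56, event-only 24.5 days.

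Over k = 0.5 to 2 the shortfall runs from 74% down to 28% at P = 60%, and from 61% down to 21% at P = 70%.

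**3. Background rates, extended at constant hazard.**
- 71% by day 42: λ = −ln(0.29)/42 = 0.02947, F(56) = 0.808; cohort 23.5 days, event-only 17.6 (25% lower).
- 65% by day 28: λ = −ln(0.35)/28 = 0.03749, F(56) = 0.878; cohort 18.5 days, event-only 15.4 (17% lower).

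The gap is then about 6 and 3 days.

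**4. Subgroups.** Two equal groups have cumulative hazards H and H × HR at day 56, with H solved so that the mean event proportion is P. At constant hazard:

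| P, HR | Group event percents | Cohort medians (gap) | Event-only medians (gap) |
|---|---|---|---|
| 60%, 1.47 | 53, 67 | 51.4, 35.0 (16.4) | 22.8, 20.6 (2.2) |
| 70%, 1.45 | 63, 77 | 38.7, 26.7 (12.0) | 21.3, 18.6 (2.6) |

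Across k = 0.5 to 2 and both rows, the cohort gap is 7.9 to 25.4 days and the event-only gap 1.7 to 2.6 days. The event percents still differ by 14 points.

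**5. What the crude percents give for first use.** Take constant hazard, random dropout d by day 56, no intermittent gaps, and participants lost before use counted as No. With a = −ln(1 − P) and b = −ln(1 − d), the Yes percent is [a/(a + b)] × [1 − exp(−(a + b))]. One minus the abstinent percent, with missing days counted as use, is 1 − (1 − P)(1 − d).
- True 60%, d = 20%: 55% and 68%. With d = 30%: 52% and 72%.
- True 70%, d = 20%: 64% and 76%. With d = 30%: 61% and 79%.

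The two figures bracket the true value. With no dropout they agree with it.

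**6. Precision of the added estimate.** At n = 360 without dropout, 1.96 × √(P(1 − P)/360) is 5.1 points at 60% and 4.7 at 70%.

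**The case against.** The case for leaving the plan alone has weight. The footnotes disclose the restriction. Censoring is handled in Figures 2 to 7 and in the Cox models. The shells use the statistics that SAP 5.0 prescribes, and the Total columns meet the undertaking in SAP 2.3 to report outcomes in the overall sample. Several stronger readings are tempting, and the documents do not support them:

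- **That no overall event percent is planned.** The Yes/No rows give one. For first use, the abstinence rows of Tables 17 to 19 give another at weeks 1, 4 and 8; read with SAP 6.0, they count missing days as use. Together they bracket cumulative first use. Neither adjusts for censoring or carries an interval, regular use has no abstinence-type rows, and the SAP does not say how someone lost before any reported use is classed in Yes/No.
- **That subgroup differences would vanish from the tables.** They would still show in the Yes/No percents directly above the time rows. Only the time rows shrink them.
- **That the plan breaks its own commitment.** The main objectives, "such as estimating the opioid use rate eight weeks after discharge to the community" among them, can equally mean status at week 8, which Tables 14 to 16 report overall. The statement that investigators "will interpret results with caution and use confidence intervals where possible" is made about multiple testing.
- **That the reported time would be about half the true one.** This holds only under the illustrative 60% and constant hazard. On the background rates the shortfall is 17% to 25%.

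The example Kaplan-Meier figures are also not shown, so it cannot be known whether they carry at-risk counts or confidence bands. What remains is the lack of any unconditional overall time summary and of any censoring-adjusted percent.

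**Conclusion.** The point holds as a cheap improvement, not as an error in the analysis. The only overall summary of time to first or regular use is conditional on the event. Its direction relative to the cohort median is certain when some participants are event-free at the end of full follow-up. With random dropout the same direction holds.

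The size is uncertain because the documents give neither a hazard shape nor a dropout rate. It is about 12 to 21 days at constant hazard and the plan's illustrative 60% to 70% events, and about 3 to 6 days on the background rates. Those background figures come from other programmes, and one of them counts drug use in general. The modelled day-56 figures suit first use better than regular use. SAP 5.2 dates regular use to the first day of a seven-day run, so no onset can be observed in about the last six days of a 56-day record.

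**What to change.** In Tables 8 to 13, in every column including Total:
- Add the Kaplan-Meier median with a 95% confidence interval, allowing an entry of not reached.
- Add the Kaplan-Meier event percent with a 95% confidence interval. For first use, give it at days 7, 28 and 56. For regular use, set each horizon to the last day on which a seven-day run can still be observed.
- Add a row for participants censored before the final horizon, beside Yes/No, and state how participants lost before any reported use are counted there.
- Label the existing time rows as conditional on having had the event.

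Add one pooled Kaplan-Meier curve per outcome. As an editorial correction, align Table 11 footnote 6 with footnotes 8 and 9; a participant without a seven-day run has no time to regular use to summarise.

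The cost is a few rows in six shells, two figures and one footnote. The subgroup Kaplan-Meier fits are already planned for Figures 2 to 7, the pooled fit uses the same data, and nothing new has to be collected.
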